**Optimizing the Effectiveness of Routine Post-Treatment Surveillance
in Prostate Cancer Survivors**

National Clinical Trial (NCT) Identification Number: NCT02957357

Principal Investigator: [name]

20 Dec 2016

Study Protocol and Statistical Analysis Plan

Specific Aim 1: Compare patient-centered outcomes (including survival, procedures/tests, treatments) in prostate cancer survivors followed with alternative surveillance frequencies.

Hypothesis: More frequent surveillance increases the receipt of additional procedures and tests in all groups of patients, but improves survival only in patients with high-risk prostate cancer.

Synopsis: We will analyze data from the National Cancer Data Base (NCDB), which includes real-world prostate cancer treatment, surveillance and outcomes data on ~70% of US patients. We will compare the effectiveness of the three most common surveillance frequencies (PSA testing every 3 months vs. 6 months vs. 12 months) stratified by risk of recurrence and initial treatment (surgery or radiation).

Introduction: The primary goal for PSA surveillance after prostate cancer treatment is to detect recurrent cancer, thus allowing provision of additional treatments which can improve survival.^{1,2} Intuitively, patients who are most likely to recur after initial treatment (“high risk” cancer) may require more frequent surveillance, while those least likely to recur (“low risk”) may require less frequent surveillance. Further, patients treated by surgery vs. radiation may require different surveillance frequencies because the definitions of recurrence differs by treatment, and false positives from surveillance PSA are much more common after radiation.^{3,4} These considerations underlie the rationale to examine outcomes separately in 6 individual groups based on *standard definitions* of recurrence risk⁵ and initial treatment:

- Low-risk prostate cancer (defined by clinical stage \leq T2a, PSA <10, and Gleason score \leq 6): Recurrence risk is <10%.⁶ Two cohorts will be examined separately, 1) those treated with **initial prostatectomy**, and 2) those treated with **initial radiation** (including external radiation and/or brachytherapy).
- Intermediate-risk prostate cancer (defined by clinical stage T2b-c, and/or PSA 10-20, and/or Gleason 7): Recurrence risk is ~30%.⁷ Two cohorts will be examined separately, 3) those treated with **initial prostatectomy**, and 4) those treated with **initial radiation**.

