- High-risk prostate cancer (defined by clinical stage \geq T3, PSA >20, or Gleason 8-10): most aggressive type of prostate cancer. Recurrence risk is ~50%.⁷ Two cohorts will be examined separately, 5) those treated with **initial prostatectomy**, and 6) those treated with **initial radiation**.

[figure not shown]
The objective of this aim is to quantify the potential benefits (survival) and harms (procedures/tests, treatments) of different PSA surveillance frequencies in the 6 patient groups, which are currently unknown. It is intuitive that more frequent surveillance will lead to more findings of elevated PSA, thus leading to more downstream procedures and tests, and treatments; with unclear survival benefit. The *rationale* for this aim is that successful completion of the proposed research will contribute novel, currently unavailable, data to inform patient decision-making.

Comparators [RQ-5]: We selected our comparators of surveillance frequency based on published recommendations and by engaging diverse stakeholders (including clinicians who specialize in prostate cancer care). The three most common surveillance frequencies in clinical

practice are every 3, 6, or 12 months. In each of the 6 patient groups, patient outcomes of every 3 vs. 6 vs. 12 month surveillance will be directly compared. We will define our surveillance groups based on the number of PSA tests patients receive during the first year following completion of prostatectomy or radiation therapy (Figure) – using an “intention to treat” approach – and analyze patient outcomes from Years 2-10. Operationally, we will compare the outcomes of patients who have 1 vs. 2-3 vs. ≥ 4 PSA tests within the first year. We selected this timeframe as we believe that these patterns would be reflective of the physician’s intended surveillance schedule as opposed to later years which may be more reflective of patient adherence to surveillance recommendations.

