accredited center, with purposeful sampling in order to achieve approximately the same overall sample size in each of the 6 risk group x treatment cohorts. By randomly selecting a small number of patients from a large number of institutions, we can ensure a broadly representative sample of hospitals and patients, ideal for CER.

Outcomes [RQ-6]: The NCDB annually collects vital status (survival), cancer status (disease free or recurrence), date of recurrence, and treatments for recurrent cancer. This will allow for evaluation of our primary outcome of overall survival, and secondary outcomes of time to recurrence and treatment for recurrent cancer. Additional secondary outcomes will be collected by the special studies mechanism, and include: rates and types of procedures (e.g. biopsy) and tests (e.g. advanced imaging), results of these tests, and treatment for recurrent cancer.

The special studies mechanism will also confirm existing NCDB information regarding cancer status and date of recurrence. Specifically, the PSA dates and results will be abstracted from medical records. Therefore, the investigators are able to define recurrence per standard definitions. These citations provide official definitions for biochemical recurrence after radiation treatment¹⁶ and radical prostatectomy.¹⁷

Cancer registry staff will review hospital and provider records to collect these data, using the same rigorous procedures as primary registry data with specific instructions and training for abstraction by the investigative team and personnel at CoC. These data will be combined with the existing NCDB data to provide the analysis dataset. This Table summarizes the data elements (outcomes) to be collected using the special studies mechanism: (Table 1)

Data Point	Format
Date of imaging	mm/dd/yy
Type of imaging performed	1) bone scan; 2) CT scan; 3) MRI; 4) X-ray; 5) PET scan; 6) other
Date of biopsy/procedure	mm/dd/yy
Biopsy/procedure results	1) benign; 2) malignant; 3) indeterminate
Date of treatment for recurrence	
Type of treatment	1) radiation; 2) surgery; 3) hormone therapy; 4) chemotherapy; 5) other therapy; 6) no treatment

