The analysis is stratified by two important factors, risk of recurrence (low, intermediate, high) and type of initial treatment (surgery, radiation); thus, 6 separate analyses will be performed. All outcomes will be defined from years 2-10 from end of prostatectomy or radiation treatment (Figure 1). We will use two modeling strategies to evaluate our outcomes of interest: 1) modified Poisson/binary regression^{19,20} with sandwich standard errors to estimate risks of the events of interest during a set follow-up period; and 2) Cox Proportional Hazards regression [CI-3]. Using the modified Poisson/binary regression models, we will estimate the risk of experiencing the outcome of interest (death, recurrence, use of procedures and tests, treatment for recurrence) during a defined interval beginning in the second year following treatment. Additionally, we will estimate overall survival using adjusted Cox Proportional Hazards regression models. We will evaluate the proportional hazards assumption by generating Kaplan-Meier survival curves and through testing interactions between relevant covariates and time in the Cox model. Covariates that violate the proportional hazards assumption will be used as stratification variables as appropriate. In sensitivity analyses, we will generate a propensity score (where the patient, provider and hospital characteristics measured at the time of prostatectomy or radiation completion are included in the propensity score) and create a matched cohort of patients to evaluate using Kaplan-Meier survival models [described in detail in C3]. For secondary outcomes, time to recurrence will be modeled for each surveillance frequency using a competing risk analysis as described by Fine and Gray.²¹ Similar methods will be used to calculate the cumulative incidence of procedures and tests and treatment for recurrence.

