Several outside/environmental factors can affect a patient's surveillance frequency. In our preliminary analysis using the US population-based Surveillance, Epidemiology and End Results (SEER)-Medicare dataset, we found race, marital status, and regional socioeconomic determinants (high school graduation rate) to be associated with different PSA surveillance frequencies. The NCDB captures a comprehensive list of covariates (see above). We will examine if surveillance frequency is associated with each individual factor and account for these factors using modeling as above. Finally, we recognize that there may still be important unmeasured confounders in our study; therefore, we plan to use sensitivity analyses to estimate the impact of a hypothetical unmeasured/unobserved confounder, using similar methodology used in a prior study by the co-I ([name]).²² This analysis will allow us to determine the extent of confounding that would substantively change our study findings.

A conceptual diagram (directed acyclic graph) demonstrating the relationship between measured covariates and our selected study outcomes for Aim 1 is provided in Figure 2 below.

Figure 2. Directed Acyclic Graph for the Hypothesized Relationship between Selected Study Variables and Outcomes for Aim 1

Footnote: Analyses will be stratified by the type of initial treatment (surgery, radiation) and recurrence risk (low, intermediate, high) and the hypothesized relationships may vary somewhat by each clinical scenario. Relationship between variables identified as pertaining to Aim 2 are noted in Figure 3.

Statistical power: There are >1,400 CoC-accredited hospitals. With 10 patients sampled at each hospital, we expect 14,000 patients will be available for analysis. We will intentionally sample approximately the same number of patients in each of the 6 cohorts (risk group x primary treatment), providing 2,333 patients in each cohort. Within each cohort, patients receiving different surveillance frequencies will be compared. Based on preliminary analysis of SEER-Medicare data, the national patterns of PSA surveillance in the first year are: (Table 2)

Number of PSAs	Low Risk	Intermediate Risk	High Risk
1	20%	18%	17%
2-3	61%	59%	53%
4	19%	23%	30%

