Power calculations used a range of 10-year overall survival rates from 70-80%, $\alpha=.05$, and two-sided test. Using distributions in Table 2, there is >80% power to detect a 5% survival difference among groups of different surveillance frequencies. Our stakeholders have indicated this level of survival difference to be meaningful.

Potential problems and alternative strategies:

Although the analysis will stratify by prostate cancer risk status, it is possible that within each

risk strata, patients with clinical and pathological features that are associated with a worse prognosis may be followed more frequently than patients with a better prognosis. One way we have proposed to address this issue is with instrumental variable analysis (Page 11). We will test two commonly-used, potential instrumental variables: region and the provider's most commonly used surveillance regimen (commonly called “provider preference”). Another way to address this in our primary analysis is to account for risk variables (clinical and pathological features) within each risk strata. We will plan to incorporate this in the primary analysis as control variables within the outcome models or within the propensity score model, as appropriate to the research question.

Our definition of comparison groups is based on published recommendations and stakeholder guidance. However, schedules for surveillance PSA tests in this observational cohort may not precisely match the anticipated 3, 6, and 12 month intervals. Multiple classification schemes will be assessed for characterizing the surveillance intervals, as described on page 2. The analysis will be repeated using alternative classification schemes, and sensitivity analyses will be used to determine if there are meaningful differences in the results based on classification of surveillance intervals, and to optimize our classification of surveillance frequency [IR-5].

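### Aim 1: the stated >80% power for a 5% survival difference is not reached by within-cohort comparisons of 5 points (39-74% pairwise, 31-75% for the three-group test)

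*Combined protocol and SAP*

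**What the plan says.** Overall survival is the primary outcome of Aim 1 (Outcomes: "This will allow for evaluation of our primary outcome of overall survival"). The Comparators section says: "In each of the 6 patient groups, patient outcomes of every 3 vs. 6 vs. 12 month surveillance will be directly compared". The groups are defined by 1, 2-3, or at least 4 PSA tests in the first year. Data Analysis stratifies by risk level and initial treatment: "thus, 6 separate analyses will be performed".

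The Statistical power section starts from the total sample: "With 10 patients sampled at each hospital, we expect 14,000 patients will be available for analysis". Sampling is balanced over the six cohorts, which gives 2,333 patients each, and the surveillance groups are compared within a cohort. Table 2 gives the expected shares. The inputs are 10-year survival of 70-80%, alpha .05 and a two-sided test. The conclusion is: "Using distributions in Table 2, there is >80% power to detect a 5% survival difference among groups of different surveillance frequencies". The section adds that stakeholders regard a difference of this size as meaningful.

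The section does not name the test, the sample size used, whether the comparison is pairwise or across three groups, or which groups differ by 5%.

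**The concern.** A cohort of 2,333 is large, but Table 2 splits it unevenly. The two outer groups hold only 17-30% each, roughly 400 to 700 patients, and a 5-point difference at 70-80% survival is small for groups of that size.

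The hypothesis makes this matter. It predicts that more frequent surveillance "improves survival only in patients with high-risk prostate cancer". Support for that statement rests partly on finding no difference in low- and intermediate-risk cohorts. A reader told that each comparison has more than 80% power for 5 points may take a non-significant result there as evidence against a meaningful difference. If the true power is nearer one half, that inference fails. The documents name no test between cohorts that would guard against it.

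**Working it through.** **Inputs.** Cohort size 14,000/6 = 2,333; Table 2 shares; 10-year survival 70-80%; two-sided alpha .05; difference of 5 percentage points. Group sizes (share x 2,333) for 1 / 2-3 / at least 4 tests:

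- Low risk: 467 / 1,423 / 443
- Intermediate: 420 / 1,377 / 537
- High: 397 / 1,237 / 700

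**Pairwise power.** Two methods were used, with the better survival assigned to either group.

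Two-proportion test: power = Φ[(d − 1.96·SE0)/SE1], where SE0 uses the pooled rate and SE1 the separate rates (an unpooled version was also run). Example, low risk, 1 vs at least 4 tests, 75% vs 80%: SE0 = 0.0277, SE1 = 0.0276, so Φ[(0.05 − 1.96 x 0.0277)/0.0276] = Φ(−0.155) = 44%.

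Log-rank (Schoenfeld): power = Φ[|ln HR|·√(D·a·(1−a)) − 1.96], where HR = ln S1/ln S2, D is expected deaths and a is the share in one group. Example, high risk, 2-3 vs at least 4 tests, 75% vs 80%: HR = 1.289, D = 1,237 x 0.25 + 700 x 0.20 = 449, a = 0.639, so Φ(2.59 − 1.96) = 73%.

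Range over methods and directions, at 70 vs 75% and 75 vs 80%:

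| Cohort | 1 vs 2-3 | 2-3 vs ≥4 | 1 vs ≥4 |
|---|---|---|---|
| Low | 54-64% | 52-63% | 39-44% |
| Intermediate | 50-60% | 58-68% | 40-46% |
| High | 48-57% | 65-74% | 42-50% |

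No cell reaches 80%. For 80% pairwise power a cohort would need about 2,740 to 6,420 patients, depending on the pair. At 2,333 the difference detectable with 80% power is 5.4-8.1 points with both rates inside 70-80%, or 4.9-8.8 if one rate may fall outside.

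**Three-group test.** Noncentral chi-square, 2 df, λ = Σ n_i(p_i − p̄)²/[p̄(1 − p̄)], and the log-rank equivalent. With the largest gap 5 points and all rates in 70-80%:

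- Stepped in frequency order: 31-40%. Example, low risk at 70/72.5/75: λ = 2.85, power 31%.
- One group apart from the other two: 41-75%. The maximum is high risk with the 2-3 group apart at 75 vs 80% (λ = 8.37, 74% by chi-square; 75% by log-rank).

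Simulation with 200,000 runs agrees at the extremes: 39% and 72% pairwise, 31% and 74% three-group.

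**Readings that do reach about 80%.**

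- Three-group test at 70/75/80 in frequency order: 89-94%, with 10 points between the outer groups.
- Rates of 80 vs 85%: high-risk 2-3 vs at least 4 tests, 78-82%; three-group test with the 2-3 group apart, 79-83%.
- The 2-3 group against the other two combined: 80-83% at 75/80, but 75-78% at 70/75.
- Surgery and radiation pooled within a risk level (4,667 patients): 67-95% pairwise, with 1 vs at least 4 tests still at 67-79%.

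**What a null result could show.** The 95% half-width for a difference is 1.96·√[S(1−S)(1/n1 + 1/n2)]. For 1 vs at least 4 tests in low risk at S = 0.75: 1.96·√[0.1875(1/467 + 1/443)] = 5.6 points. Over S = 70-80% this pair gives 5.2-6.0 points in low risk and 5.1-5.9 in intermediate, so even an observed zero would not exclude 5 points. The other two pairs in these cohorts have half-widths of about 4.0-5.0 points, so an observed difference within roughly 0.1-1.0 points of zero could exclude 5 (intermediate 1 vs 2-3 at 70% survival is borderline).

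**The high-risk-only pattern by chance.** Suppose the same 5-point difference and base rate held at all three risk levels. Within one treatment, the chance of significance in high risk alone is P(high)·[1 − P(low)]·[1 − P(int)]. For 1 vs at least 4 tests at 75 vs 80% this is 0.49 x 0.56 x 0.54 = 15%. Over pairs and base rates it is 8-16%, against 0.8 x 0.2 x 0.2 = 3.2% if each test had 80% power, so about 2.5 to 5 times as often.

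**The case against.** The strongest reply is that this is under-description rather than wrong arithmetic. The sentence speaks of a difference among groups, there are three groups, and 70/75/80 spans the stated survival range in 5-point steps. The three-group test then has 89-94% power in every cohort, using only the plan's figures. That reading cannot be ruled out, and it may be how the figure arose. It does not rescue the claim, because 5 points is presented as the meaningful difference and the power would come from a 10-point gap between the outer groups. The 2-3-versus-rest contrast is not named in the plan, and pooling departs from the six separate analyses.

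Two further points have some force. The 8-16% figure is an illustration that assumes equal effects and base rates and a reading by significance alone; the plan states no such decision rule. And the planned Poisson and Cox models yield risk and hazard ratios, so comparing an interval with 5 points requires adjusted risk or survival differences, which the plan does not name. Neither point changes the power figures.

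It is also fair that the sample follows from 10 patients per centre at more than 1,400 centres, so correcting the sentence will not change the number of patients.

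**Conclusion.** The concern holds. For the within-cohort comparisons the plan describes, with a 5-point difference and rates in 70-80%, power is 39-74% pairwise and 31-75% for the three-group test. The stated figure of more than 80% is reached only under a wider gap, a rate outside 70-80%, a contrast the plan does not name, or pooling.

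The calculation assumes complete 10-year follow-up, no covariate adjustment, no site clustering, no missing data and no multiplicity correction. Follow-up is in fact 8-10 years. Assuming constant hazards, deaths counted from year 1 and follow-up uniform over 8-10 years, log-rank pairwise power falls from 40-74% to 33-64%, so on follow-up the figures above are if anything optimistic. The data remain useful; it is the stated power, and any reading of null results that leans on it, that needs correcting.

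**What to change.** In the Aim 1 Statistical power section:

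- Name the test, sample size, contrast and pattern of differences behind the power statement.
- Replace the single figure with power per cohort and comparison (about 39-74% pairwise for 5 points), or with the difference detectable at 80% power (5.4-8.1 points with both rates in 70-80%), and state the follow-up assumed.
- Do not substitute a figure for all 14,000 patients pooled. It assumes one common effect in all cohorts, contrary to the hypothesis.

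In Data Analysis, add that each cohort's confidence interval for each comparison will be judged against 5 points, and that a non-significant result is read as no meaningful difference only if the interval excludes 5 points. State that the interval is for an adjusted difference in survival or risk, derived from the planned models. Note that for 1 vs at least 4 tests in low and intermediate risk the expected half-width is about 5.1-6.0 points.

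The cost is a rewritten power paragraph, one sentence on interpretation and one additional summary from models already planned. No extra patients or data are needed. The drawback is a less favourable stated power.

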In sensitivity analysis, we will vary this timeframe to define surveillance frequency based on the timing of the first PSA test following completion of prostatectomy or radiation therapy (first PSA within 3 months vs. >3 but within 6 months vs. >6 months); or define comparison groups empirically (most frequent 1/3 of patients vs. middle vs. least frequent 1/3 of patients) – to assess if our findings are robust to these varying exposure groupings [IR-5]. We will also explore using Years 1-2 to define surveillance frequency, and examining patient outcomes from Years 3-10.

Figure 1. Sample Identification and Definition of Timeframes for Measurement

Data Source [IR-1][DR-2][PC-2]: The National Cancer Data Base (NCDB) is a joint program between the Commission on Cancer (CoC) of the American College of Surgeons and the American Cancer Society.⁸ NCDB, started in 1989, is a nationwide cancer outcomes database that includes $>1,400$ CoC-accredited cancer programs and $\sim 70\%$ of all newly diagnosed cancer cases in the US – making its data broadly generalizable and ideal for CER.⁸⁻¹⁰ Systematic, longitudinal follow-up data are updated annually, with multiple data-quality assurance steps taken. **The high quality and representative NCDB data are used for the annual US “cancer statistics” report.**^{11,12} Thus, our results using the NCDB optimizes external validity and generalizability. Data elements are recorded by certified cancer registrars using nationally standardized data item and coding definitions specified by the Facility Oncology Registry Data Standards. Detailed information about data elements collected by the NCDB, standardized data collection protocol, and quality control methods used to assess reported case information is available at: www.facs.org/cancer/ncdb/datasubmission.html.

NCDB Special Study mechanism for primary data collection will be used to obtain the detailed level of information required for this study on data elements which do not currently exist in the NCDB registry – including PSA frequency – and to fill in missing data [MD-1].¹³⁻¹⁵ This will be done using chart abstraction by each of the CoC-accredited centers. For this Aim, the NCDB will randomly select 10 prostate cancer patients diagnosed in 2005-07 from each CoC-

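### Aim 1 leaves room to re-choose the surveillance-frequency classification after outcome results are seen; if that were done freely, the per-test false-positive rate could rise from 5% to roughly 11–19%

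*Combined protocol and SAP*

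**What the plan says.** All references are to the combined protocol and SAP.

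- **Specific Aim 1, Comparators.** Groups are formed from the count of PSA tests in the first year after treatment: 1, 2–3, or ≥4. The reason given does not involve outcomes: first-year testing is thought to show what the physician intended, while later testing may show patient adherence.
- **Same section, sensitivity analysis.** Two alternatives are listed: timing of the first PSA, and empirical thirds. Their purpose is "to assess if our findings are robust to these varying exposure groupings". A third, defining exposure over Years 1–2 with outcomes in Years 3–10, is to be explored.
- **Specific Aim 1, Potential problems and alternative strategies.** Real testing may not match 3-, 6- and 12-month schedules, so "The analysis will be repeated using alternative classification schemes". Sensitivity analyses are then given two purposes: to find out whether results differ meaningfully, and "to optimize our classification of surveillance frequency".
- **Specific Aim 1, Statistical power.** Two-sided α of .05, with no adjustment across classifications.
- **C2, Specific Aim 2, Comparators.** The comparison groups are those of Aim 1.

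**The concern.** The same repeated analyses are given two incompatible jobs. A robustness check takes the primary definition as fixed and asks whether the answer survives a change of grouping. If the results of those analyses also help decide what the grouping should be, they no longer test it. The nominal 5% error rate and the confidence intervals assume that the groups were set without reference to the outcome.

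The design does not supply blinding by default. Patients were diagnosed in 2005–07, the registry collects vital status every year, and survival through 2015 is expected by the time of analysis. PSA frequency is not in the registry and must be abstracted for this study. Outcome data can therefore already be in hand when exposure groups are formed, and only a written rule keeps the two apart. A changed definition would affect up to six separately analysed cohorts and, through the shared comparison groups, the anxiety and quality-of-life comparisons of Aim 2.

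**Working it through.** **The plan's own figures.** 1,400 hospitals × 10 patients = 14,000, and 14,000 / 6 = 2,333, which agrees with "providing 2,333 patients in each cohort". The plan states no false-positive rate across classifications, so the only baseline is its α of .05. Its power statement is a separate matter and does not bear on this point.

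**Inputs from the document.** N = 2,333 per cohort. Death risk 25%, the middle of the range implied by 10-year survival of 70–80% (Statistical power). Four three-level schemes (Comparators): Year-1 count, timing of first PSA, empirical thirds, Years 1–2.

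**Inputs assumed.** The document does not say how strongly the schemes overlap. The range taken for latent correlation with the Year-1 count was 0.3–0.7 for first-PSA timing and 0.6–0.9 for Years 1–2, with thirds cut from the same score as the count.

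**Step 1, definition fixed.** With the Year-1 count kept as primary, the rate is α = 5% per test. Simulation under no effect gave 4.5–5.4% for that definition.

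**Step 2, bound without overlap.** If k independent schemes are tried and any with p < .05 may be reported, the rate is 1 − (1 − α)^k.

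- k = 3: 1 − 0.95³ = 0.143, and 0.143 / 0.05 = 2.9 times nominal.
- k = 4: 1 − 0.95⁴ = 0.185, and 0.185 / 0.05 = 3.7 times nominal.

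These schemes share PSA data, so independence overstates the rate.

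**Step 3, with overlap.** Null cohorts of 2,333 were simulated, and the share with p < .05 under at least one scheme was counted.

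| Schemes open to choice | Rate per test | Multiple of 5% |
|---|---|---|
| Year-1 count only | 5% | 1 |
| 3, overlapping | 11–13% | 2.2–2.6 |
| 4, overlapping | 14–17% | 2.8–3.4 |
| 3, independent | 14.3% | 2.9 |
| 4, independent | 18.5% | 3.7 |

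A separate simulation generated PSA dates from patient-specific testing rates (lognormal, median 2.6 per year, 3,000 cohorts at each of two degrees of spread). It gave 13.8% and 16.0% for four schemes, with each scheme alone at 4.5–5.2%.

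**Step 4, one scheme for all cohorts.** Step 3 lets each cohort choose its own scheme. When a single scheme is chosen for all six cohorts to maximise the number of rejections, the rate per test is about 12–13% under similar assumptions, against 15–17% with free choice in each cohort.

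**Limits.** Monte Carlo standard error in Step 3 is about 0.5 to 0.9 percentage points, depending on the simulation. The tests were unadjusted group comparisons, not the planned Cox and modified Poisson models. Covariates, site clustering and the Years 3–10 outcome window were not modelled.

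**The case against.** The strongest reply is that the plan never says the primary definition may be replaced. It names the Year-1 count beforehand, justifies it without reference to outcomes, and repeats in the potential-problems section that the groups come from published recommendations and stakeholder advice. That section points back to the schemes already listed as sensitivity analyses. The difficulty it addresses is misclassification, so optimizing may mean no more than mapping PSA dates better to 3-, 6- and 12-month schedules, which needs no outcome data.

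Most of this stands. A reader might infer that the investigators intend to pick whichever cut points give the preferred survival contrast; no sentence says so. What does not fall away is the sentence itself. Sensitivity analyses are the means for both purposes, and the first purpose is a comparison of results. Read literally, results may feed back into the definition. The innocent reading is available, but nothing in the text secures it.

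**Conclusion.** The point holds as a gap in the wording: outcome-based choice of the exposure definition is left open, not prescribed. Under free selection on significance the rate per test could be roughly 11–19%. The lower end comes from three overlapping schemes and the upper from four independent ones. All the overlap figures rest on assumed correlations.

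Three stronger readings are not supported:

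- **That the plan triples its false-positive rate.** About threefold is a worst-case size. If the named definition is kept, the multiple is 1.
- **That this inflation applies separately in each of six cohorts and for every outcome.** The plan sets out the same comparators for all six groups, and a common scheme points toward the lower end of the range. The calculation concerns one test in one cohort and does not include the separate multiplicity of cohorts and outcomes.
- **That effect estimates are shown to be biased away from the null.** No such bias was calculated.

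The change is still worth making, because the present text allows a use of results under which the nominal error rate would not hold.

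**What to change.** In Specific Aim 1, Potential problems and alternative strategies:

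1. Delete the clause ending "to optimize our classification of surveillance frequency", or limit it to refinement based on PSA-date data alone, examined blind to outcomes.
2. State that the Year-1 count classification (1 vs 2–3 vs ≥4) remains primary in all six cohorts whatever the sensitivity analyses show. Aim 2 then inherits the same fixed groups.
3. State that every alternative scheme will be reported as a sensitivity analysis whatever it shows.

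The cost is one or two sentences of wording. No data or planned analysis is lost. If better mapping of test dates was all that was meant, the change simply records it.
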